5. STUDY STRENGTHS AND LIMITATIONS

Strengths

A major strength of this study is that use of THIN enables analysis of an extensive sample of PPI users that is representative of the UK primary-care population, with a similar age and sex distribution to those in the national population supporting a broad external validity of our findings and generalizability. Also, we will analyze the risk in another drug class (H₂RA) that share similar treatment indication than PPI to verify the specificity of the results. Validation of the outcome with the PCP will help to reduce the extent of outcome misclassification when working with automated databases.

Limitations

A potential limitation of the study is that acid suppressing drug use could be misclassified in some instances. For example, the recording of a PPI prescription in THIN does not necessarily mean that the patient actually took the medication, although it is likely that patients with repeating prescriptions do take their medication as there is a prescription almost every month. Also, lack of recording of OTC acid suppressing drugs is another source of misclassification (PPI available as OTC June 2009 on UK market). This misclassification of drug exposure will most likely be non-differential and thus will bias the effect estimates towards the null. Therefore, it should be noted that to the extent

such misclassification occurs in our study population, our effect estimates will tend to underestimate the true risk. As with any medication, PPI users might differ from non-users in a number of characteristics, such as treatment indication, severity of the treatment indication, co-morbidity, etc. Like in all observational studies, there is always the possibility for some remaining confounding not amenable to adjust after all our efforts in the design and analyses.

Outcome missclassification of seizure will be substantially reduced with our two step validation process: first obtaining free text comments for the review of the patient profiles and second the direct validation with the PCP. The extent of recording of comorbidity, medication use and life style habits in THIN will help to minimize as much as possible potential confounding by any these variables.

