3. STUDY OBJECTIVES

- To estimate the incidence of seizure in the general population and stratified by epilepsy status
- To estimate the relative risk of seizure associated with use of PPI and H₂RA and stratified by epilepsy status.

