4.8 Exposure definition

We will categorize medication use in the nested case-control analysis as follows: *current use* when the supply of the most recent prescription lasted until the index date; *recent use*, when the supply of the most recent prescription ended 1–90 days before the index date; *past use*, when the supply of the most recent prescription ended 91–365 days before the index date; and non-use, when there was no recorded use of the relevant medication in the 365 days before the index date.

Current users of PPI at index date will be further analyzed according to duration of treatment (continuous use on PPI therapy will be defined as the sequence of consecutive PPI Rx without presenting at least one break (gap of 30 days or greater between the end of supply and the start of supply of two consecutive Rx). Dose-response among current users of PPI will also be analyzed. Similar classification scheme will be applied to users of H₂RA.

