4.9 Statistical analysis

Incidence rate of seizure overall as well as age and sex-specific will be computed in the study cohort.

A nested case-control analysis will be performed to assess the effect of acid-suppressing drugs and potential risk factors for seizure using unconditional logistic regression. In this analysis all patients ascertained with an incident episode of seizures will be used as

cases. The control group will comprise a random sample of study cohort members, frequency-matched by calendar year (described in section 4.6). Under our study design of incidence density sampling, the odds ratio (OR) is an unbiased estimator of the incidence rate ratio (RR) (Rothman 2002).

To determine the association between study outcome and current use of PPI and H₂RA, we will run unconditional logistic regression models and compute the OR and their 95% confidence intervals (95%CI). The estimates will be adjusted for the frequency-matched variable (calendar year), age, sex, time to event and other independent risk factors described in section 4.7.

Sub-analyses will be repeated in the strata of individuals with epilepsy and individuals free of epilepsy for descriptive purposes.

Statistical analyses will be performed using Stata package version 11.0 (StataCorp LP, College Station, TX, USA).

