4.9.1 Sample size

Assuming an experience of 100,000 person-years among PPI current users, 100,000 person-years among non users of PPI and an incidence rate of seizures of 50 per 100,000 person-years among non users of PPI and a true relative risk of one, a 95% CI would extend to 1.48 if the estimated ratio is 1. We expect to accumulate larger person-time experience than mentioned above both among current users of PPI and non users.

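### The H2RA analysis is meant to verify that a PPI result is specific, but the protocol plans a separate odds ratio for each class and no estimate of the difference between them

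*Protocol*

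**What the plan says.** Section 5 of the protocol, like the strengths paragraph of the synopsis, gives the reason for studying H2RAs: they are a class "that share similar treatment indication than PPI to verify the specificity of the results".

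The objective in section 3 is "To estimate the relative risk of seizure associated with use of PPI and H₂RA and stratified by epilepsy status". It names no comparison of one class with the other.

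Section 4.8 sorts use into current, recent, past and non-use. The last is defined as "non-use, when there was no recorded use of the relevant medication in the 365 days before the index date". For the second class it adds: "Similar classification scheme will be applied to users of H₂RA".

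Section 4.9 then states: "To determine the association between study outcome and current use of PPI and H₂RA, we will run unconditional logistic regression models", reporting ORs with 95% CIs adjusted for the section 4.7 factors. It names no reference category. The only comparator named in a calculation is in section 4.9.1: "Assuming an experience of 100,000 person-years among PPI current users, 100,000 person-years among non users of PPI".

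The protocol contains no PPI-versus-H2RA contrast, no criterion for specificity, no rule for people using both classes and no precision statement for H2RA.

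**The concern.** A stated purpose and the described analysis do not meet. Verifying specificity requires knowing how far the PPI association differs from the H2RA association, and how precisely. The plan yields two separate estimates and leaves the difference unestimated.

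Two features make this more than a matter of presentation:

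- **Unequal precision.** If there is less H2RA use than PPI use, the H2RA interval will be wider. The same true effect can then give an interval that excludes 1 for one class and includes 1 for the other.
- **Possibly different reference groups.** Non-use refers to the drug in question. Unless both classes enter the same model, H2RA users can sit in the PPI reference group and PPI users in the H2RA reference group. The two ORs are then not on a common footing.

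Section 5 itself concedes that PPI users may differ from non-users in indication and its severity. A comparison between two classes with similar indications is the plan's main handle on that problem, so it should be estimated. The final report goes to the regulator, where a specificity statement would carry weight.

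**Working it through.** **1. Reproduce the protocol's own figure (section 4.9.1).** Inputs: 100,000 person-years in PPI current users and in non-users, 50 seizures per 100,000 person-years, true ratio 1.

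- Expected events per group: 100,000 × 50/100,000 = 50.
- SE of the log rate ratio: √(1/50 + 1/50) = 0.20.
- Upper 95% limit: exp(1.96 × 0.20) = 1.48.

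The stated 1.48 is correct, but it covers PPI against non-use only.

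**2. Precision of the between-class ratio.** Take one model with disjoint exposure groups and a common reference with E₀ events. Each log OR has variance 1/E + 1/E₀, and their covariance is 1/E₀, so the reference cancels:

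SE[log(OR_PPI / OR_H2RA)] = √(1/E_PPI + 1/E_H2RA).

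H2RA person-years are an assumption and are shown as a range. E_PPI = 50, the rate is 50 per 100,000 in both classes, and the true ratio is 1.

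| H2RA person-years (assumed) | H2RA events | SE | 95% CI, PPI vs H2RA | Upper limit with 4 controls per case |
|---|---|---|---|---|
| 100,000 | 50 | 0.200 | 0.68-1.48 | 1.55 |
| 50,000 | 25 | 0.245 | 0.62-1.62 | 1.71 |
| 25,000 | 12.5 | 0.316 | 0.54-1.86 | 2.00 |
| 10,000 | 5 | 0.469 | 0.40-2.51 | 2.79 |

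The last column multiplies the SE by √(1 + 1/4), using the minimum control ratio in section 4.6.

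**3. What two ORs side by side can suggest.** Suppose the true ratio against non-use is 1.5 for both classes. Non-users have 50 events and PPI users 50 × 1.5 = 75. Control sampling is ignored.

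- PPI: SE = √(1/75 + 1/50) = 0.183, giving 1.50 (1.05-2.15).
- H2RA at an assumed 25,000 person-years: 12.5 × 1.5 = 18.75 events, SE = √(1/18.75 + 1/50) = 0.271, giving 1.50 (0.88-2.55).
- Ratio: SE = √(1/75 + 1/18.75) = 0.258, giving 1.00 (0.60-1.66).

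Identical effects produce one interval that excludes 1 and one that does not. At an assumed 10,000 H2RA person-years, the H2RA interval is 0.70-3.23 and the ratio interval 0.47-2.12. At 100,000, both class intervals are 1.05-2.15 and the pattern disappears, so it depends on H2RA use being the smaller.

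**4. Can a reader recover the ratio from the two ORs?** Not its interval. Treating the two ORs as independent at 25,000 person-years gives SE = √(0.0333 + 0.0733) = 0.327 instead of 0.258. The covariance from a single fit is needed.

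**The case against.** The strongest reply is that a contrast between two coefficients is ordinary detail for an analysis plan, which is not at hand, and that section 4.9 delivers the objective in section 3. Specificity appears only among the strengths. This is partly right: the main PPI OR is unaffected. But the protocol itself advertises the check and describes an analysis that does not carry it out, so the point does not rest on a missing detail alone.

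Four stronger readings are tempting, and the documents do not support them.

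- **That specificity will be judged by significance.** The protocol describes no significance testing; it plans ORs with 95% CIs, and its sample-size section concerns interval width. The misreading in step 3 is a foreseeable risk only.
- **That comparison with non-use is stated.** It is inferred from sections 4.8 and 4.9.1.
- **That both ORs carry the same confounding by indication, or that the direct contrast is the least affected estimate.** Section 4.7 lists GERD and peptic ulcer antecedents as covariates, and nothing shows that severity is equal across the classes. Confounding is plausibly shared in part.
- **That the direct contrast should replace the two ORs.** A ratio near 1 cannot separate neither class raising risk from both raising it equally. The introduction reports seizure-related signals for both PPIs and H2RAs, so H2RA is not an established inert comparator. The ORs against non-use must stay.

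It is also fair to say that the contrast may be too imprecise to settle the matter. That is a reason to report the interval.

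**Conclusion.** The point holds in limited form. The protocol claims a check of specificity, but as written it produces no estimate of the difference between classes, and its definition of non-use leaves open whether the two ORs share a reference. The specificity claim is therefore unsupported; the class-specific ORs remain valid for the stated objective.

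The size depends on H2RA person-time, which the protocol does not give. Over an assumed 100,000 down to 10,000 H2RA person-years, data with a true ratio of 1 would leave between-class ratios from 0.68-1.48 to 0.40-2.51 unexcluded, and wider ranges once control sampling is counted. These figures assume 100,000 PPI person-years, equal rates of 50 per 100,000, disjoint exposure groups in one model and no covariate adjustment. Section 4.9.1 expects more PPI person-time than this, which would narrow the intervals somewhat, but the smaller H2RA group would still dominate. The change should be made, though it does not threaten the main result.

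**What to change.** In section 4.9, specify one model with a joint exposure variable: current PPI only, current H2RA only, current use of both, recent or past use of either, and non-use of both as reference. Add a rule for people who switch between classes, since section 4.8 classifies each class separately.

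From that model, report:

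1. the OR for current PPI-only use against non-use of both;
2. the OR for current H2RA-only use against non-use of both;
3. the ratio of the first to the second, with a 95% CI from the model covariance.

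State that any conclusion on specificity will cite the ratio together with both ORs, and will not rest on one interval excluding 1 while the other does not.

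The cost is one derived variable, a classification rule, one linear contrast and a few sentences, with no new data. The report must acknowledge two limits: the ratio may be imprecise if H2RA users are few, and it reduces confounding by indication without removing it, because severity may differ between the classes.

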6. PROJECT FORMALITIES AND TIMELINES

6.1 Privacy and confidentiality

Privacy issues will be addressed and respected at each stage of the study. All analyses and reporting will be done on appropriately de-identified data and only in aggregate form. AstraZeneca will not receive any patient or provider identifiable information from at any time. We will abide by the Guidelines for Good Pharmacoepidemiology Practices (GPP, 2007). The study protocol is dependent on approval by the ethical review board Multicenter Research Ethics Committee (MREC) for studies performed in THIN.

6.3 Study reporting

The final analyses and study report is estimated to be delivered within 20 months of external approval from ethic committee assuming 3 months for anonymization of free text comments by the external provider of THIN data (AIS) and 3-4 months for obtaining questionnaires from PCPs, aiming at high response rate (around 80-90%) with anonymization of all information. At least one manuscript based on the findings of this project will be submitted for publication to a peer-reviewed journal.

6.4 Data management

will comply with all applicable data protection, security and privacy laws, rules and regulations with respect to the collection, production, use, processing, storage, transfer, modification, deletion, and/or disclosure of any information related to this study

under this Agreement. will ensure that information is not disclosed or transferred to any third party not mentioned in this protocol. will ensure that appropriate technical and organizational measures are taken to protect information against accidental or unlawful destruction or accidental loss or alteration, or unauthorized disclosure or access and against all other unlawful forms of processing. will store the Database used to perform this study at the premises of

Provided estimated timelines for the conduct of the observational study on the association between acid-suppressing drugs and seizures are based on the Principal Investigators (PI's) experience in performing similar pharmacoepidemiology studies with the THIN database.

The timeline of submission of the final report is estimated to be delivered within 20 months after protocol approval and include the following main steps:

Cumulative time period (mths)	Activity	Time AIS * (external provider) of THIN data, mths)	Time PI (mths)
	Ethical approval for studies performed in THIN; MREC (Multicenter Research Ethics Committee)		
	Quality checking of information in database		
	Searches in database to identify potential cases and request for free text comments of the identified potential cases		
	Anonymization of free text comments		

	Manual review of computerized records and free text comments (blinded to all exposure information) to identify remaining potential cases for which requests are made to send questionnaires to the general practitioner (GP)		
	AIS to send questionnaire to GP, aiming at a high response rate (around 80-90 %). Anonymization of data.		
	PI to review all anonymized information from questionnaires, copies of additional information the GP deemed to be related to the outcome of interest (hospital summaries, consultant referral letters and results of laboratory test) and the computerized profiles to assign case status (blinded for exposure information)		
	Analyses and draft report provided to AZ		
	Final report to be delivered to AZ and AZ to submit to MHRA		

Figure 1. Study design
